3.1.3 Follow-up Phase

Aim 1: No intervention

Aim 2: No intervention

Aim 3: All RCT participants will have a 6-month follow-up visit. Participants in the intervention arm will be able to attend the follow-up visit if they attend at least one of the health coaching visits. For both arms, the follow up visit will consist of the same data collection (CASI and chart abstraction) as the 3-month visit.

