3.3 Study Duration, Enrollment and Number of Sites

3.3.1 Duration of Study Participation

Aim 1: Study duration for Aim 1 will be two days, as the first day participants will complete the CASI at time of consent, and the second day (scheduled based on participant availability, they will complete the virtual or in-person focus group or in-depth interview).

Aim 2: Study duration for Aim 2 will be one day for completing all the activities.

Aim 3:

Pilot phase: We will use pilot testing over a projected 3-month period to ensure that intervention critical steps are primed for implementation. Over one month, we aim to recruit n=10 participants. Pilot phase participants will follow the same study procedure timeline as participants randomized to the coaching intervention arm of the RCT, excluding the 6-month follow-up visit, and will not be followed in the RCT or contribute outcome data. At the end of every health coaching visit (the baseline, 1-week, 1-month and 3-month visits), pilot phase participants will complete a brief feedback interview to ensure face validity and identify areas needing refinement. Following this phase, we will systematically review

feedback and adapt the study design and strategy as needed prior to the RCT, with amendments submitted to the IRB as needed for modifications to study design.

Intervention phase: Study duration for Aim 3 will consist of data collection and health coaching visits over a 6-month period (see Table 1: Schedule of Study Procedures for Aim 3 RCT), with the baseline visit as the study's start. Visit windows, as described in Table 1, show that the 1 week visit window is +7/-5 days, the 1 month visit window is + 30/- 14 days, the 3-month visit window is + 30/- 14 days, and 6-month visit window is +/- 30 days.

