5.1.3.3 Electronic Medical Record Review

As part of the study, the study team will review the CHOP medical record of the participants for particular variables:

- STI test dates
- STI diagnoses
- STI medications including PrEP
- Mental health diagnoses: derived from the problem list in the general EPIC chart.
 No data will be accessed from protected mental health encounters.

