For Aim 3, all participants will be patients of CHOP primary care clinics, and thus can be rapidly referred to clinicians and social workers in case there is a need to intervene for an identified mental health issue. Our mood rating instrument, the PSC-17, does not include any assessment of suicidal ideation. However, if a participant discloses suicidal ideation, homicidal ideation, or abuse during an intervention session, the PI will be notified immediately, as well as the clinic social worker. Based on clinician assessment, participants who report suicidal ideation will be referred to the local Emergency Department or psychiatric crisis center, as needed. Any reports of child abuse will be reported to the clinic social worker and reported to ChildLine in accordance with Pennsylvania State Law. All participants will be provided mental health resources at the end of the first session, irrespective of their score on the PSC-17.

Participants will complete a modified version of the Adverse Childhood Experiences survey. To minimize the risk to participants that may arise regarding fear of disclosing a specific form of adversity, the study will utilize a modified version of the ACES questionnaire that has been validated in middle and high school students. The modified inventory is presented in 7 items. Within each item, participants are presented with a diagram including 2-4 circles. Each circle contains the description of an ACE, with language adapted from the cited inventories. The wording has been modified to be appropriate for the reading and comprehension abilities of 14 to 18-year-olds. Participants are instructed to read the ACE description contained in each circle, to think back on their entire life, and to decide if the

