6.2 Secondary Endpoints

Aim 1: None

Aim 2: None

Aim 3:

- Referral feasibility: # potential participants referred/# eligible.
- Recruitment feasibility: # enrolled/# patients referred.
- Retention feasibility: # completing all sessions/# enrolled.
- Acceptability: Assessed at the final visit by a Coaching Satisfaction Survey
- Secondary outcomes:
 - a) Repeat STI test results at three-months and six-months.
 - b) Prevention behavior, including uptake of PrEP, condom use, HIV testing, and partner notification of positive STI results

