- Retention feasibility: Calculated as the proportion of participants who completed each follow-up coaching session over the total number of scheduled coaching visits. To determine if the mental health is associated with retention, I will use logistic regression to compare proportions of subjects retained between the following participant groups: high depressive symptoms, high trauma score, and substance abuse (see definitions in exploratory analysis section above), adjusting for demographic characteristics such as race and sex.

Fidelity will be assessed by reviewing baseline visit transcripts for the first ten participants and reviewing a random sample of 2 visits per week for ongoing supervision

- We will use the Motivational Interviewing Assessment-Supervisory Tools for Enhancing Proficiency (MIA-STEP) cut offs for fidelity: interventionist will have to demonstrate in the first ten sessions the use of at least half of the MI consistent items three to four times, namely, receive a “Somewhat” (4) frequency and extensiveness rating and at least an “Adequate” (4) skill level rating. In other words, the interventionist has to show capacity to use a moderate amount of MI strategies and skills and show an adequate level of performance when implementing them.
- On random sample, if three successive sessions occur in which they fall below proficiency standards, the interventionist will receive additional training, feedback, and coaching until he or she demonstrated again the minimal MI proficiency standards. Supervisors may elect to use the protocol’s MI proficiency standards as a supervisory benchmark for their clinicians. The MIA-Step MI rating worksheet tool (see below) will be used to assist in this task (<https://motivationalinterviewing.org/sites/default/files/mia-step.pdf>)
- In addition, the interventionist will complete the content checklist after each visit to assure each psychoeducation content domain (e.g. condoms, partner notification) was addressed in the session.
- Acceptability: I will calculate the proportion of participants who endorse each item on the Coaching Satisfaction Survey in the "agree" or "strongly agree" range.

Exploratory outcome analyses: Utilization of prevention behavior at the six-month time point. I will calculate the proportion of participants who:

- Initiate PrEP
- Do not develop repeat sexually transmitted infection (STI)
- Report 100% condom use
- Receive HIV testing
- Report partner notification of their initial STI

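### Chart abstraction is listed as part of the 3- and 6-month visits, with no common cut-off day and no rule for non-attenders, so repeat-STI and PrEP outcomes may be missing or cover unequal time

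*Combined protocol and SAP*

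**What the plan says.** Section 3.1.3 (Follow-up Phase, Aim 3) describes the 6-month visit: "For both arms, the follow up visit will consist of the same data collection (CASI and chart abstraction) as the 3-month visit". Table 1 has chart abstraction only in the baseline, 3-month and 6-month columns, for both arms. Section 3.3.1 gives the windows: "the 3-month visit window is + 30/- 14 days, and 6-month visit window is +/- 30 days".

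Section 3.1.3 first promises a 6-month visit to every RCT participant. It then adds, for one arm only: "Participants in the intervention arm will be able to attend the follow-up visit if they attend at least one of the health coaching visits". SOC has no such condition.

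Section 5.1.3.3 describes the record review on its own terms: "the study team will review the CHOP medical record of the participants for particular variables". The variables are STI test dates, STI diagnoses, STI drugs (PrEP among them) and mental health diagnoses. The section sets no attendance condition, look-back or end date. Section 5.3 says that in Aim 3 "all participants will be patients of CHOP primary care clinics", and Section 3.1.1 has the team checking the STI database daily for recruitment.

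Section 6.2 lists "Repeat STI test results at three-months and six-months" as a secondary outcome, with PrEP uptake among the prevention behaviours. Section 6.3.2 puts PrEP initiation and absence of repeat STI under "Utilization of prevention behavior at the six-month time point", as proportions of participants. It gives neither a day range nor a defined denominator. Intention to treat is stated for the primary analysis only. Section 4.4 classes a participant who misses a visit as a no-show for it and does not mention the chart.

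**The concern.** The hospital record can be read whether or not a participant comes to a research visit. A missed visit costs the survey, but it need not cost the chart outcomes. By listing abstraction as visit content and giving no rule for non-attenders, the plan leaves staff free to skip those charts, and to decide differently from one participant to the next in an unblinded trial.

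The attendance condition makes this more than a symmetric nuisance. If charts are abstracted only when the visit takes place, the coaching participants with no session at all drop out of the 6-month chart outcomes, while equally disengaged SOC participants do not. Sections 3.1, 3.2 and 9.1.1 already provide for a move to 2:1 randomisation should coaching participants prove hard to retain, so unequal attendance is a contingency that the plan itself foresees.

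Time at risk is a second gap. A count of events by six months needs an end day. If it is the actual visit date, two participants with the same underlying risk can be observed for quite different lengths of time.

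**Working it through.** The plan gives no figure for repeat STI or PrEP, so there is none to reproduce. The checks are window arithmetic and two illustrations.

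**Inputs from the documents.** Windows of +30/−14 days at 3 months and ±30 days at 6 months (Table 1, Section 3.3.1); day 0 at the baseline visit, where randomisation occurs (Sections 3.3.1 and 9.1.1); 150 participants, 75 per arm, with up to 10% lost (Section 6.4).

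**Assumptions.** Nominal days 90 and 180; a six-month repeat-STI risk of 10% to 40%; a constant hazard; the loss rates and visit-date gap named below.

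**1. Spans of the visit windows.**
- 3 months: 90 − 14 = 76 to 90 + 30 = 120. Span 44 days, ratio 120/76 = 1.58.
- 6 months: 180 − 30 = 150 to 180 + 30 = 210. Span 60 days, ratio 210/150 = 1.40.
- With nominal days 91 and 183 the spans are unchanged and the ratios are 121/77 = 1.57 and 213/153 = 1.39.

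**2. Charts at stake.** At the plan's 10% loss, 0.10 × 150 = 15 participants would have no chart outcome if abstraction followed attendance. This is an upper limit on what the fix recovers, because some of those charts will contain no STI test.

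**3. How far missing charts could move a risk difference.** Let p be the risk among those observed in each arm, and a and b the missing fractions in the coaching and SOC arms. The coaching-minus-SOC difference then lies between (1−a)p − [(1−b)p + b] and [(1−a)p + a] − (1−b)p. With p = 20% assumed:
- a = b = 10%: 18 − 28 = −10 points, to 28 − 18 = +10 points.
- a = 20%, b = 5% (assumed): 16 − 24 = −8 points, to 36 − 19 = +17 points.

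These are extreme bounds, not expected biases.

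**4. Effect of unequal time.** With risk R by day 180, h = −ln(1−R)/180 and risk(t) = 1 − exp(−ht).

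| R by day 180 | risk at day 150 | risk at day 210 | risk(190) − risk(170) |
|---|---|---|---|
| 10% | 8.4% | 11.6% | 1.1 points |
| 20% | 17.0% | 22.9% | 2.0 points |
| 30% | 25.7% | 34.0% | 2.8 points |
| 40% | 34.7% | 44.9% | 3.4 points |

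The middle columns are the extremes for an individual. The last column is the shift in an arm comparison if one arm were seen on average at day 170 and the other at day 190. The documents give no reason to expect such a gap. Detection also clusters at test dates, which a constant hazard ignores, so the table is illustrative only.

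**The case against.** The strongest reply is that the documents are silent rather than wrong. The section that governs the record review sets no attendance condition, and the no-show rule does not mention charts. A sensible team would abstract everyone. STI test dates are collected, so an analyst could truncate at any common day. The outcomes are secondary or exploratory, and Section 6.3.2 only calculates proportions, with no between-arm test specified.

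Much of this stands. A reader might infer that the plan commits to discarding the charts of no-shows. It does not; that loss follows only if abstraction is carried out as visit content and nothing more. A reader might also infer that follow-up differs between the arms. It differs between participants if counting stops at the visit, and it biases a comparison only if visit timing differs by arm. The retention problem is stated conditionally, not as an expectation. The attendance condition should not be over-read either: the first coaching session is at baseline, so it affects only those who attend none of the four sessions, a number the documents do not give.

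Nor can the chart outcomes be called the only ones free of self-report and retention. Referral and recruitment counts are free of both. Repeat STI partly depends on attendance, since Section 7.1 has both arms returning at 3 months for repeat testing, and an untested participant is not known to be STI-free.

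What does not stand is that test dates alone solve the timing. Truncation at a common day works only within the abstracted period. If one chart was closed at day 150, no common day after 150 is available for everyone. Nor does silence protect the denominator, since intention to treat is not extended to these outcomes.

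**Conclusion.** The point holds as a gap in the rules for the chart outcomes. Abstraction is listed under visits with 44-day and 60-day windows; 6-month attendance carries a condition in the coaching arm only; and no common cut-off or rule for non-attenders is given. Repeat-STI and PrEP outcomes may therefore be missing for non-attenders, possibly selectively in the coaching arm. They may also cover 150 to 210 days (up to 1.4-fold) at six months, and 76 to 120 days at three, if counted to the visit.

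The size rests on reading abstraction as tied to the visit. On that reading, up to 15 of 150 participants are affected at the plan's own 10% loss. A 20-day gap in mean visit date, which is assumed, would shift a comparison by 1.1 to 3.4 points for risks of 10% to 40%. For PrEP, the point applies where the chart is the source; the plan does not say whether chart or survey decides.

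The primary GSES analysis takes nothing from the chart and is unaffected. The change is still worth making, because the missing data and unequal time are avoidable at almost no cost.

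**What to change.** In Section 3.1.3, Table 1 and Section 5.1.3.3, state that charts are abstracted for every randomised participant, regardless of visit or coaching attendance, unless authorisation for chart review is withdrawn.

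In Section 6.3.2:
- Count PrEP initiation and repeat STI by arm, from randomisation to one fixed day per time point, for example the nominal days 90 and 180, using recorded test and prescription dates. Section 5.1.3.3 names dates for STI tests only, so add the PrEP prescription date.
- Use all randomised participants as the denominator.
- Report the number tested per arm, so that an untested participant is not read as STI-free.
- Flag any SOC participant who received the coaching session offered after study completion (Section 7.1) before the cut-off. A control seen at day 150 could be coached before day 180. Extending the cut-off to day 210 would widen that exposure.

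The cost is protocol wording and a few extra chart reviews, and each abstraction must wait until its cut-off day has passed. There is no added burden on participants. Tests or prescriptions that never reach the hospital's record will still be missed.

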3.2 Allocation to Treatment Groups and Blinding

Aim 1: N/A

Aim 2: N/A

Aim 3: Non-stratified 1:1 randomization will occur at baseline using the REDCap randomization tool based on randomization tables. The study team will not be able to change study groups for participants once randomization has taken place. The randomization will not be blinded to the participants or the study team because of the nature of the intervention.

As mentioned in Section 3, if difficulty retaining coaching participants during the RCT generates a disparity in evaluable participants per arm, the RCT's randomization scheme will be changed to 2:1, intervention vs SOC, to balance numbers of evaluable participants per arm.

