Aim 3: We will conduct 1) an iterative pilot phase followed by 2) a small RCT assessing intervention effect on the intermediate target of prevention self-efficacy. Pilot testing will occur over a 3-month period to prime intervention for implementation, with the aim of recruiting n=10 pilot participants. Pilot phase participants will follow the same study procedure timeline as participants randomized to the coaching intervention arm of the RCT, excluding the 6-month follow-up visit. Pilot participants will not be followed in the RCT or contribute outcome data. At the end of every health coaching visit (the baseline, 1-week, 1-month and 3-month visits), pilot phase participants will complete a brief feedback interview to ensure face validity and identify areas needing refinement. Feedback will be incorporated into the study design, with amendments submitted to the IRB as needed. The RCT will randomize youth with recent STI 1:1 to the coaching intervention vs a standard of care (SOC) control. If difficulty retaining coaching participants during the RCT generates a disparity in evaluable participants per arm, the RCT's randomization scheme will be changed to 2:1, intervention vs SOC, to balance numbers of evaluable participants per arm. Both arms (intervention and SOC) will have data collection visits at the baseline, the 3-month, and the 6-month-follow-up time points. In addition, the intervention group will have health coaching sessions at baseline, 1 week, 1 month and 3 months. At the end of the 3-month health coaching visit, a sample of RCT phase participants assigned to the intervention arm will complete a brief feedback interview to ensure face validity and identify areas needing refinement for future studies.

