3.3.2 Total Number of Study Sites/Total Number of Subjects Projected

The study, including all three aims, will be conducted at investigative sites in the United States. For Aim 1, participants will be recruited from two clinics affiliated with the Children's Hospital of Philadelphia (CHOP) that house Title X adolescent family planning clinics, Karabots Care Network and Cobbs Creek Care Network, from the Adolescent Specialty Clinic, and by word-of-mouth referral from existing participants. For Aim 2, participants will be recruited from two clinics affiliated with the Children's Hospital of Philadelphia (CHOP) that house Title X adolescent family planning clinics, Karabots Care Network and Cobbs Creek Care Network. For Aim 3, participants will be recruited from Children's Hospital of Philadelphia (CHOP) primary care clinics.

Analysis and study coordination will occur at the Roberts Center for Pediatric Research of the Children's Hospital of Philadelphia.

Aim 1: Recruitment goal for Aim 1 is 50 participants, recruited in groups of 5-8 for virtual or in-person focus groups or in-depth interviews. Once this number is reached, recruitment will stop.

Aim 2: Recruitment goal for Aim 2 is 25 clinicians, clinic staff, and administrators are recruited from the primary care clinics. Once this number is reached, no more providers will be recruited.

Aim 3: Recruitment goal for the pilot phase is 10 participants. Recruitment goal for the RCT is 150 participants, 75 for each arm (with the chance of more participants in the RCT's intervention arm than control arm if there are changes to the randomization scheme).

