6.3.2 Analysis

Aim 1: We will conduct a deductive qualitative analysis of focus group transcripts and in-depth interview transcripts with our theoretical model guiding the coding process. Codes related to model constructs will be assigned to interview segments to organize the data, using the software NVivo, with two study team members separately reviewing the first 10 transcripts line by line, assigning codes as concepts become apparent. We will compare text segments to those that have been previously assigned the same code, and to segments coded separately by each analyst, to decide whether they reflect the same concept. We will use this process to generate a coding scheme, then apply it to all transcripts. Once coding is complete, we will review the data to document emerging themes-general insights gleaned from the entirety of the data- which may inform intervention content.

Aim 2: Survey data will be summarized via descriptive statistics. We will set a >80% threshold for high acceptability, feasibility and appropriateness. The interview coding process will parallel that described in Aim 1. We will use an integrated deductive and inductive coding approach. Transcripts will be reviewed using deductive methodology, where CFIR determinants will be used as the coding framework. After completion, the transcripts will be re-reviewed using inductive methodology where codes identifying novel barriers and facilitators of implementation that do not map onto the CFIR will be identified and used to develop a coding framework that is then applied to all transcripts. We will integrate the qualitative and quantitative data by merging findings through a comparative coding analysis. The AIM and FIM scores will be dichotomized (completely disagree/disagree vs completely agree/agree). We will compare the distribution of content themes between providers with high vs low acceptability and, separately, high vs low feasibility ratings. Data will then be used as a starting point in which to build an optimized PrEP-inclusive coaching implementation strategy to be tested in the subsequent RCT.

Aim 3: The primary analysis will be based on an intention to treat approach and will include all subjects randomized at Visit 1.

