6.4 Sample Size and Power

Aim 1: The individual focus group size of 5-8 is informed by consensus methods literature. The goal of the pooled focus group size of ~50 is thematic saturation. The goal of the in-depth interviews is thematic saturation, which could be reached at ~15 participants. If we do not reach saturation at this sample size, or if key themes emerge among subgroups of participants which we wish to further explore, we will continue focus groups and in-depth interviews until saturation is met.

Aim 2: Previous studies demonstrate that 3-6 charts per clinician are sufficient for reliable and valid assessment in CSRs. We propose to interview 25 clinicians and nurses with the goal of achieving saturation of themes, for which this sample size should be sufficient, and will continue if saturation is not met.

Aim 3: We propose a sample size of 150 participants (75 intervention, 75 control – with the possibility of a greater number of intervention than control if we shift to 2:1 randomization) based on the aim of detecting a moderate effect size score difference in the change in modified GSES scores between intervention and control. Given this sample size, and assuming a range of intra-subject correlations across subjects ranging from (0.01 to 0.3), we will have 80% power and a two-sided alpha of 0.05 to detect a 0.7-0.9 standard deviation difference change in GSES scores from baseline and six months by treatment group. And be protected from and up to 10% lost-to-follow-up rate.

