9 STUDY ADMINISTRATION

9.1 Treatment Assignment Methods

9.1.1 Randomization

Aim 3: Simple 1:1 randomization will occur at baseline using the REDCap randomization tool. The randomization tables will be created by a statistician that is not a part of the study team. The study team will not take part in randomization. Participants will complete the baseline CASI before being randomized. The study team will not be able to change randomization after it is applied in REDCap.

As mentioned in Section 3, if difficulty retaining coaching participants during the RCT generates a disparity in evaluable participants per arm, the RCT's randomization scheme will be changed to 2:1, intervention vs SOC, to balance numbers of evaluable participants per arm.

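### The move to 2:1 evens out evaluable numbers at only one retention ratio per switch point, barely changes precision, and does not replace six-month follow-up of everyone randomised

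*Combined protocol and SAP*

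**What the plan says.** Allocation starts equal: "Non-stratified 1:1 randomization will occur at baseline using the REDCap randomization tool based on randomization tables" (Section 3.2). Section 3.1 attaches a contingency, "If difficulty retaining coaching participants during the RCT generates a disparity in evaluable participants per arm", and Sections 3.2 and 9.1.1 repeat it. The response is that "the RCT's randomization scheme will be changed to 2:1, intervention vs SOC, to balance numbers of evaluable participants per arm". None of these sections says how large the disparity must be, when it is judged, by whom, or what makes a participant evaluable.

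The total is not raised. Section 6.4 reads "We propose a sample size of 150 participants (75 intervention, 75 control", and Section 3.3.2 foresees only a different split, "with the chance of more participants in the RCT's intervention arm than control arm if there are changes to the randomization scheme". The one loss figure in the plan is the allowance of up to 10% in Section 6.4, which is not divided by arm.

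The primary analysis in Section 6.3.2 is by intention to treat and "will include all subjects randomized at Visit 1". The outcome is change in the modified GSES from baseline to six months. Section 3.1.3 first says that all RCT participants have a six-month visit. It then opens that visit to intervention participants who attended at least one coaching visit, and sets no such condition for SOC.

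**The concern.** The clause answers loss of participants from one arm by randomising more people to that arm. Three things are at stake.

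- **Balance.** A fixed 2:1 suits one degree of disparity. With no trigger or timing stated, it may be applied to a disparity that it overcorrects.
- **Precision.** Equal evaluable numbers are not in themselves a gain for the primary comparison, so the change may bring little.
- **Bias.** If those who leave coaching differ from those who stay, adding participants changes the counts but not the selection. Only the missing six-month scores can address that, and Section 3.1.3 closes the six-month visit to some intervention participants.

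**Working it through.** **Inputs from the plan.** Total 150, planned 75/75 (Section 6.4); 1:1 at first, 2:1 for those randomised after the switch (3.2); total unchanged (3.3.2).

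**Assumptions.** SOC retention 90%, taken from the 10% allowance in 6.4. Coaching retention 80%, 70%, 60% or 45%. Switch after s = 30, 75 or 100 randomised. The plan gives none of the arm-specific rates or switch points. Counts are expected values, so fractions remain.

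**The plan's own figure.** The plan gives no figure for numbers or precision under 2:1. The nearest is in 6.4: "we will have 80% power and a two-sided alpha of 0.05 to detect a 0.7-0.9 standard deviation difference change in GSES scores". With 67 per arm (75 less 10%) and the SD of change equal to √(2(1-ρ)), the detectable difference is (1.96 + 0.84) × √(2(1-ρ)) × √(2/67). This gives 0.68 SD at ρ = 0.01 and 0.57 SD at ρ = 0.3. The lower end of the stated range is nearly met and the upper end is not reached. The range errs on the conservative side, and nothing below depends on it.

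**Step 1, arm sizes.** n_HC = s/2 + 2(150-s)/3 and n_SOC = s/2 + (150-s)/3.
- s = 30: 15 + 80 = 95 and 15 + 40 = 55
- s = 75: 37.5 + 50 = 87.5 and 37.5 + 25 = 62.5
- s = 100: 50 + 33.3 = 83.3 and 50 + 16.7 = 66.7

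**Step 2, balance point.** Equal evaluable numbers need r_HC/r_SOC = n_SOC/n_HC:
- s = 30: 55/95 = 0.58
- s = 75: 62.5/87.5 = 0.71
- s = 100: 66.7/83.3 = 0.80

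**Step 3, gap and variance.** Evaluable numbers are n × r. Relative variance is 1/(n_HC r_HC) + 1/(n_SOC r_SOC), divided by its value at 75/75. For 80%/90% with s = 75: 1/70 + 1/56.25 = 0.03206, against 1/60 + 1/67.5 = 0.03148, a ratio of 1.018. Cells show coaching v SOC (gap); variance ratio.

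| Retention, coaching/SOC | 1:1 throughout | Switch after 100 | Switch after 75 | Switch after 30 |
|---|---|---|---|---|
| 80/90% | 60 v 67.5 (-7.5) | 66.7 v 60 (+6.7); 1.006 | 70 v 56.25 (+13.75); 1.018 | 76 v 49.5 (+26.5); 1.060 |
| 70/90% | 52.5 v 67.5 (-15) | 58.3 v 60 (-1.7); 0.998 | 61.25 v 56.25 (+5); 1.007 | 66.5 v 49.5 (+17); 1.041 |
| 60/90% | 45 v 67.5 (-22.5) | 50 v 60 (-10); 0.990 | 52.5 v 56.25 (-3.75); 0.994 | 57 v 49.5 (+7.5); 1.019 |
| 45/90% | 33.75 v 67.5 (-33.75) | 37.5 v 60 (-22.5); 0.975 | 39.4 v 56.25 (-16.9); 0.971 | 42.75 v 49.5 (-6.75); 0.981 |

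The rule widens the gap in 3 of the 12 switch cells and narrows it in 9. For a switch after 75, the two gaps are equal when 67.5 - 75r = 87.5r - 56.25, so r = 123.75/162.5 = 0.76. The rule therefore narrows the gap once coaching loss passes about 24%.

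**Step 4, the most that allocation could gain.** Variance is smallest at n_HC/n_SOC = √(r_SOC/r_HC). That ratio is 1.06, 1.13, 1.22 and 1.41 for the four rows, and the variance saving over 1:1 is then 0.1%, 0.4%, 1.0% and 2.9%. No allocation within 150 does better.

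**Step 5, bias.** If a share 1 - r of the coaching arm has no six-month score, the observed mean differs from the mean of all randomised by (1 - r) × (mean of those observed - mean of those missing). The arm size does not appear, so more allocation leaves it as it was. The mixed model can use baseline and three-month scores, but that help does not depend on allocation either.

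**Step 6, sections side by side.** Section 6.3.2 analyses everyone randomised. Section 3.1.3 bars from the six-month visit anyone randomised to coaching who attended no coaching visit. Section 3.2 links retention of coaching participants to evaluability without defining it. The three do not fit together.

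**The case against.** The clause is meant to balance numbers, not to add precision, and over much of the assumed range it does so. A reader might infer that it fails to balance the arms at most plausible drop-out rates. The documents do not support that: they give no arm-specific loss rate, and the table shows a smaller gap in 9 of 12 cells. A switch after 30 is also doubtful if evaluable means six-month data, since Aim 3 runs over 12 to 18 months (Section 3.1). With a switch after 100, even 80%/90% ends slightly closer to balance (6.7 against 7.5).

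A reader might also infer that 2:1 is efficient only if SOC retention is four times coaching retention. That describes 2:1 from the first participant. Here the cumulative ratio after a switch at 75 is 87.5/62.5 = 1.4, which is close to optimal when SOC retention is about twice coaching retention.

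A third tempting reading is that the plan counts anyone who stops coaching as non-evaluable. The plan does not say so. Evaluable is undefined, and one attended session, including the one at baseline, keeps the six-month visit open. The conflict with intention to treat therefore reaches only those who attend no session, who may be few. Nor is anyone moved out of SOC, because assignments already made cannot be changed.

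Finally, feasibility and acceptability belong to Primary Aim 3, and more coached participants would serve them. Multi-channel outreach already exists (Section 4.4), and both arms are paid for the six-month visit (Section 9.7). All of this stands. It narrows the point, but it does not give the clause a useful effect on the primary analysis or settle the conflict between Sections 3.1.3 and 6.3.2.

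**Conclusion.** The concern holds in a limited form. Within 150 participants a mid-trial move to 2:1 balances evaluable numbers at one retention ratio per switch point. It enlarges a small disparity if made early or midway and reduces a larger one. Which of these happens depends on a trigger and timing that the plan does not set. Variance changes by about -3% to +6% across the cases shown, so the clause is close to neutral for precision rather than harmful. It cannot correct bias from selective loss in the coaching arm. The conditional six-month visit in Section 3.1.3 conflicts with the intention-to-treat population in Section 6.3.2.

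The sizes rest on assumed retention and switch points and on a total fixed at 150. The bias argument and the conflict between sections do not depend on those assumptions. The trial is not invalidated, but the wording should be changed.

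**What to change.** - Reconcile Sections 3.1.3, 3.2 and 6.3.2: state that every randomised participant is followed for the six-month GSES whatever coaching was attended, and remove the attendance condition on that visit.
- Define evaluable for the primary outcome as having a six-month GSES.
- If six-month completion falls behind in the coaching arm, respond with outcome-only follow-up through the existing REDCap, phone and text channels.
- Keep 1:1 for all 150 and remove the 2:1 clause from the abstract and Sections 3.1, 3.2, 3.3.2, 6.4 and 9.1.1.

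The cost is mainly wording, plus a little more follow-up effort. The real downside is fewer coached participants for the feasibility and acceptability summaries if loss is heavy: 75 randomised to coaching, rather than about 83 (switch after 100), 87.5 (after 75) or 95 (after 30), so up to about 20 fewer.
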